APPENDIX B. MULTIPLE IMPUTATION DETAILS**Primary Analysis****Data preparation**

Intercurrent events (ICEs) are defined in [Table 1](#) (Section 1.2.1). Visits where an ICE occurred will be labelled with the appropriate ICE type:

USUBJID	TRT01P	AVISITN	AVISIT	ADY	AVAL	CNSRDT	EVNTDESC
██████████	Placebo	4		Visit 4/ Week 1		██████████	
██████████	Placebo	5	██████████	Visit 5/ Week 2	2	██████████	Prohibited antipsychotic
██████████	Placebo	6		Visit 6/ Week 3	2	██████████	Prohibited antipsychotic
██████████	Placebo	7		Visit 7/ Week 4	2	██████████	Prohibited antipsychotic
██████████	Placebo	8		Visit 8/ Week 5	2	██████████	Prohibited antipsychotic
██████████	Placebo	9		Visit 9/ Week 6	2	██████████	Prohibited antipsychotic
██████████	Placebo	10		Visit 10/ Week 7	2	██████████	Prohibited antipsychotic
██████████	Placebo	11		Visit 11/ Week 8	2	██████████	Prohibited antipsychotic

The classification of intercurrent events (ICEs) will be performed as follows:

Event	CNSR	EVNTDESC
Early termination from randomized treatment due to "Lack of Efficacy" or an Adverse Event of "Exacerbation of schizophrenia"	1	ET due to lack of efficacy
An oral antipsychotic use was documented in the CRF (Concomitant Medication or Protocol Deviations) and reviewed in a blinded manner in the statistical data review meeting and does not meet the conditions in Section 1.2.1	2	Prohibited antipsychotic
Early termination from randomized treatment due to other reasons	3	ET due to other reasons

Multiple Imputation Method

[figure not shown]
Parameter Estimation Model

Imputation of ICE data under MAR

Imputation of ICE data under MNAR

[figure not shown]

Analysis model

[figure not shown]
Tipping Point Analysis (Two dimensional)

Tipping Point Analysis (One dimensional)

[figure not shown]
[figure not shown]
[figure not shown]
[figure not shown]
[figure not shown]
The above process will be repeated, but the delta value for the placebo group will be held at zero. The range of delta values and increments may be adjusted post hoc depending on the observed treatment effect in order to most effectively characterize the “tipping point”.

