6.7. Prior and Concomitant Medication or Therapy

Any prior or concomitant medication a patient has had within 30 days before IMP administration and up to the end of study, including FU, will be recorded on the CRF. Trade name and international nonproprietary name (if available), indication, dose, and start and end dates of the administered medication will be recorded. The sponsor will encode all medication according to the World Health Organization drug dictionary.

The following medications will be prohibited during this study:

- antipsychotics other than the study treatment
- strong or moderate inhibitors of CYP1A2 within 14 days or 5 half-lives (whichever occurs last) prior to randomization
- strong inducers of CYP1A2 within 30 days prior to randomization
- dopamine reuptake inhibitors or prescription psychostimulants
- opiates or opiate-containing analgesics within 14 days prior to randomization
- In addition to those listed above, medications that may be expected to significantly interfere with the metabolism or excretion of olanzapine, may be associated with a significant drug interaction with olanzapine, or may pose a significant risk to patients' participation in the study.

- Olanzapine (except when given according to the study protocol)

Allowed medications in this study include rescue medications (Section 6.7.1.1), protocol-approved antidepressants (including selective serotonin reuptake inhibitors [other than fluvoxamine], serotonin and norepinephrine reuptake inhibitors, and trazodone), and mood stabilizers (except carbamazepine) (Section 6.7.1.2), medications required for the treatment of any adverse events, and contraceptives as per [Appendix E](#).

Medications prescribed for the treatment of chronic medical conditions, other than antipsychotic medications, or for the treatment of acute medical conditions (such as antibiotics) may be permitted per investigator judgment.

COVID-19 and seasonal flu vaccines will be allowed during the study. Other vaccinations may be allowed after consultation with the MM or sponsor.

A partial list of additional disallowed medications is provided in [Appendix G](#). In the event that a new concomitant medication not specified in this protocol is initiated by the patient, the investigator is encouraged to approach the MM or the sponsor to discuss.

It is advised not to allow benzodiazepines and anticholinergics within 8 hours or 12 hours, respectively, of rating scales' assessments.

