1.2. Estimands for Primary and Secondary Objectives and Endpoints

1.2.1. Primary Estimand

The purpose of the primary estimand is to evaluate the efficacy of TV-44749 compared to placebo as if patients do not withdraw and adhere to treatment as instructed (see Section 3.2.1 in the Study Protocol). Patients who withdrew from the treatment/study due to lack of efficacy or did not adhere to the investigator instructions will be regarded as if they share the slope of the placebo group from that intercurrent event (ICE) time point until week 8 (see [White et al 2019](#)). Use of prohibited antipsychotic medications is considered non-adherence to the investigator instructions unless it is short term oral use.

The clinical question of interest is as follows: "What will be the treatment benefit if a patient adheres to treatment for 8 weeks?".

For the primary efficacy objective, the following estimand attributes will be employed:

- a. **Treatment:** The treatment of low (318 mg monthly [q1m]), medium (425 mg q1m), or high (531 mg q1m) dose of TV-44749 compared to placebo, separately, will be evaluated according to the randomization assignment in Period 1.
- b. **Population:** All randomized adult patients who have a confirmed diagnosis of schizophrenia, present with acute exacerbation of disease, and are eligible for olanzapine treatment.
- c. **Endpoint:** Change from baseline to week 8 in the PANSS total score.
- d. **Population-level summary:** Difference in the means between each individual dose arm of TV-44749 and placebo for the endpoint described above.

In this study any use of antipsychotic concomitant medications is regarded as prohibited per protocol (see Section 6.7 in the protocol). However, short term oral antipsychotic medications prohibited by the protocol may be occasionally used as part of the management of acute agitation of schizophrenia exacerbation in real-life clinical practice. If such case of use of oral antipsychotic occurs, it would not be considered as effecting the primary endpoint when:

- The treatment use end date was > 14 days prior to the week 8 (Visit 11) and
- Treatment duration was ≤ 3 consecutive days and
- There were only ≤ 2 treatment episodes (where a treatment episode is defined as ≤ 3 consecutive days of treatment followed by at least 7 days without treatment) from baseline to Visit 11.

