In addition, any use of prohibited antipsychotics after early termination is not considered an ICE. Prior antipsychotic medications without a defined end-date are not deemed as ICE of "prohibited concomitant antipsychotic medication" since these cases occur before randomization and initiation of treatment.

Table 1: Classification of Intercurrent Events

Intercurrent Event	Strategy	Handling of Intercurrent Events

 • Early discontinuation of treatment due to: 
 ◦ lack of efficacy ◦ disease progression • Prohibited antipsychotic (with the exception above) 	Hypothetical	Measurements after ICE will be removed and replaced with imputed data using reference-based (CIR) imputation (assuming MNAR)

 • Early discontinuation of treatment due to other reasons (including due to adverse event) 	Hypothetical	Measurements after ICE will be removed and replaced with imputed data based on randomized treatment group (assuming MAR)

 • Allowed concomitant medications • Adverse event that did not lead to treatment discontinuation • Use of prohibited medications that are not antipsychotic • Short term use of prohibited antipsychotic (see meeting the definition above) • Injection site reaction • Out of window safety assessments 	Treatment policy	Measurements after ICE will be included in the primary analysis

ICE=intercurrent event; MAR=missing at random; MNAR=missing not at random; CIR = copy increments in reference

Any data collected after the intercurrent event (ICE) of taking prohibited antipsychotic medications (except as described above) or withdrawal from randomized treatment due to insufficient clinical response (i.e., lack of efficacy) will be treated in the analysis as MNAR. An ICE of early discontinuation for other reasons will be treated in the analysis as if the patient fully complied and completed the study (i.e., assuming missing at random [MAR]); see Table 1 for further details on the classification and handling of ICEs. This complies with the hypothetical approach.

For ICEs that were not foreseen at the time of writing the protocol and that require the use of the hypothetical strategy, classification as MAR/MNAR and revisiting this classification will be done in a blinded manner on a case-by-case basis prior to database lock for efficacy and will be

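### SAP Appendix B limits the prohibited-antipsychotic code to oral use, whereas Section 1.2.1 and Table 1 set no route limit

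*SAP*

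**What the plan says.** SAP Section 1.2.1 sets a wide scope: "In this study any use of antipsychotic concomitant medications is regarded as prohibited per protocol". It then makes one carve-out: "Use of prohibited antipsychotic medications is considered non-adherence to the investigator instructions unless it is short term oral use". Three conditions on timing, duration and number of episodes define that carve-out. Table 1 lists prohibited antipsychotic use, less the exception, as an event under the hypothetical strategy: later measurements are removed and replaced by CIR imputation. Section 1.2.2 applies the same handling to CGI-S and PSP. SAP Section 17.1 describes the change from the protocol as a short oral exception and nothing more. Protocol Section 6.7 prohibits "antipsychotics other than the study treatment", with no route stated.

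Appendix B opens its data preparation with "Intercurrent events (ICEs) are defined in" Table 1 (Section 1.2.1). It then gives a three-row coding table under the words "The classification of intercurrent events (ICEs) will be performed as follows". Code 1 is termination for lack of efficacy or an exacerbation adverse event. Code 2, labelled as prohibited antipsychotic, applies where "An oral antipsychotic use was documented in the CRF (Concomitant Medication or Protocol Deviations) and reviewed in a blinded manner" and the Section 1.2.1 conditions are not met. Code 3 is "Early termination from randomized treatment due to other reasons".

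Section 6.2.3 words the same event a third way, as prohibited antipsychotics outside the management of schizophrenia, with a cross-reference to Section 1.2.1.

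**The concern.** In Section 1.2.1 the word oral belongs to the exemption. In Appendix B it has become a condition for being an event at all. The other two codes both require early termination, so no row catches non-oral use in a patient who continues.

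The primary and key secondary estimands depend on removing PANSS, CGI-S and PSP scores after prohibited antipsychotic use. A programmer who follows the coding row and a statistician who follows Table 1 would build different analysis datasets for the same patient. The SAP says that it prevails over the protocol, but no visible text ranks its body against its appendix.

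**Working it through.** The plan gives no figure to reproduce here, so the check is to run each kind of case through both rules. All cases concern use before any early termination, because Section 1.2.1 does not count later use as an event.

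| Case | Section 1.2.1 and Table 1 | Appendix B rows, read literally | Result |
|---|---|---|---|
| Oral, meets the short-term conditions | Scores kept (treatment policy) | No code, scores kept | Agree |
| Oral, fails the conditions | CIR from use | Code 2, CIR | Agree |
| Non-oral, patient stays on treatment | CIR from use | No code, later scores kept as observed | Conflict |
| Non-oral, then termination for lack of efficacy or exacerbation | CIR from use | Code 1, CIR from termination | Only scores between use and termination differ |
| Non-oral, then termination for other reasons | CIR from use | Code 3, MAR from termination | Conflict |

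The last row depends on the arm. Under Section 6.2.3, CIR follows the placebo trend from the event onward, and MAR draws on the patient's own arm.

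- Active arm: code 3 instead of code 2 changes the imputation mechanism, and scores between use and termination are also kept.
- Placebo arm: both methods draw on the placebo arm, so only the scores between use and termination differ.

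The third row can arise. Protocol Section 5.4 leaves withdrawal after a prohibited medication to the sponsor's decision in each case. Protocol Section 2.1.2 mentions a rapid-acting intramuscular olanzapine approved for acute agitation in schizophrenia, which is the setting Section 1.2.1 has in mind. That shows a non-oral product exists, not that it was used in this trial.

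Scale, from the documents' own counts:

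- Planned: 640 randomized, 1:1:1:1, so 640/4 = 160 per arm. Weight of one patient: 1/160 = 0.63%.
- Randomized by 29 January 2024 (Protocol Amendment Details): 675, so 675/4 = 168.75 per arm. Weight: 1/168.75 = 0.59%.
- Shift in a simple arm mean = (number misclassified × mean score difference) / patients per arm. One patient and a 1-point difference give about 0.006 points. With an assumed 20-point difference, one patient gives 20/168.75 = 0.12 to 20/160 = 0.13 points.

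These are simple-mean approximations. They ignore model adjustment and any knock-on effect through the imputation model.

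**The case against.** The strongest reply is that classification is a documented human decision against Table 1, not a string match on one row. Appendix B itself defers to Table 1 for the definition. Section 1.2.1 says that classification according to Table 1 will be done blinded before the efficacy lock, and Section 5.7 sends potential events to the statistical data review meeting. This stands as a reason to expect that a real case would be caught. It does not remove the conflict, because Appendix B writes the blinded review into the oral-only row itself.

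The second reply is that the harmful path is narrow. Protocol Section 5.4 also terminates patients who need another antipsychotic, and a deteriorating patient may well leave with code 1, which already leads to CIR. Section 17.1 speaks of only a few cases of early prohibited use. This too stands, and it bears on size.

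It could also be said that the all-MAR sensitivity analysis (Section 6.2.5.1) and the treatment policy analysis (Section 1.2.3) cover the matter. They show results under other handling rules, but they do not make the primary result match its own estimand.

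**Conclusion.** The contradiction is on the face of the SAP and is most likely a drafting slip. It is minor. It concerns non-oral use only; oral use is coded consistently with Table 1. The effect is probably small, its direction cannot be determined from the documents, and the number of patients affected is unknown. This assumes that the row is applied as printed. Much of the imputation text in Appendix B is not shown in the public copy, but the three-row coding table appears complete.

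A reader might infer more, in three ways, and the documents do not support any of them.

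- That the primary result is biased: no non-oral use is reported, and the blinded review may correct the coding.
- That code 3 in place of code 2 switches the imputation in every arm: it does so only for active-arm patients.
- That Section 1.2.1 opens a similar gap by exempting prior antipsychotics with no end date: the section gives its own premise, that such use precedes randomization, and Protocol Section 4.1 requires tapering of prior oral antipsychotics to finish by then.

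**What to change.** Before the efficacy database lock:

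1. Reword the code 2 row in Appendix B to: *any prohibited antipsychotic use, by any route, other than short-term oral use meeting the Section 1.2.1 conditions*.
2. State that Table 1 governs if the row and the table differ.
3. Make the phrase in Section 6.2.3 match Section 1.2.1.

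The cost is one table row, one added sentence and one phrase. No new data are needed.

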APPENDIX C. MULTIPLE COMPARISONS DETAILS

APPENDIX D. SUMMARY OF ENDPOINTS BY ESTIMAND STRATEGY FOR PERIOD 1

Family of Endpoint	Variable	Primary Estimand	Key Secondary Estimand	Sensitivity using MAR	Treatment Policy	Modified Treatment Policy
Primary	Change from baseline to week 8 in PANSS score	✓		✓	✓	✓
Key secondary	Change from baseline to week 8 in CGI-S score		✓	✓	✓	✓
	Change from baseline to week 8 in PSP score		✓	✓	✓	✓
Other Secondary		■		■	■	■
					■	■
					■	■
					■	■
					■	■
					■	■
					■	■
					■	■
					■	■
					■	■
					■	■
					■	■
					■	■
					■	■
					■	■
					■	■
					■	■
					■	■
					■	■
					■	■
					■	■
					■	■
					■	■
					■	■
					■	■
					■	■
					■	■
					■	■
					■	■
					■	■
					■	■
					■	■
					■	■
					■	■
					■	■
					■	■
					■	■
					■	■
					■	■
					■	■
					■	■
					■	■
					■	■
					■	■
					■	■
					■	■
					■	■
					■	■
					■	■
					■	■
					■	■
					■	■
					■	■
					■	■
					■	■
					■	■
					■	■
					■	■
					■	■
					■	■
					■	■
					■	■
					■	■
					■	■
					■	■
					■	■
					■	■
					■	■
					■	■
					■	■
					■	■
					■	■
					■	■
					■	■
					■	■
					■	■
					■	■
					■	■
					■	■
					■	■
					■	■
					■	■
					■	■
					■	■
					■	■
					■	■
					■	■
					■	■
					■	■
					■	■
					■	■
					■	■
					■	■
					■	■
					■	■
					■	■
					■	■
					■	■
					■	■
					■	■
					■	■
					■	■
					■	■
					■	■
					■	■
					■	■
					■	■
					■	■
					■	■
					■	■
					■	■
					■	■
					■	■
					■	■
					■	■
					■	■
					■	■
					■	■
					■	■
					■	■
					■	■
					■	■
					■	■
					■	■
					■	■
					■	■
					■	■
					■	■
					■	■
					■	■
					■	■
					■	■
					■	■
					■	■
					■	■
					■	■
					■	■
					■	■
					■	■
					■	■
					■	■
					■	■
					■	■
					■	■
					■	■
					■	■
					■	■
					■	■
					■	■
					■	■
					■	■
					■	■
					■	■
					■	■
					■	■
					■	■
					■	■
					■	■
					■	■
					■	■
					■	■
					■	■
					■	■
					■	■
					■	■
